10.1.4.2 Weaning

After the stabilization period, VentaProst weaning procedures will be initiated when the clinical team determines the patient is hemodynamically stable enough to begin the weaning process. VentaProst weaning will occur from mechanical ventilation only. The table below shows the typical weaning steps for aerosolized Veletri from mechanical ventilation. If weaning from VentaProst occurs while on mechanical ventilation, doses will be decreased in 20% increments of the VentaProst equivalent dose. If the patient has been extubated and is on institution's standard of care delivery system for administering aerosolized Veletri, weaning will occur in accordance with each site's standard of care guidelines for weaning of aerosolized Veletri.

Weaning Guideline

Aerosolized Veletri (from Ventilator)	VentaProst (from Ventilator)
50 ng/kg/min	Dose Equivalence to aerosolized Veletri 50 ng/kg/min
40 ng/kg/min	80% of Dose Equivalence
30 ng/kg/min	60% of Dose Equivalence
20 ng/kg/min	40% of Dose Equivalence
10 ng/kg/min	20% of Dose Equivalence

Patients on mechanical ventilation will be weaned from VentaProst slowly due to concern that VentaProst is providing significant clinical benefit and to avoid a rebound effect.

VentaProst weaning will be performed as per institutional guidelines for weaning of inhaled Veletri, except that VentaProst doses will be decreased in increments of 20% of the VentaProst equivalent dose, with a minimum of 30 minutes between changes, down to 20% of the dose before discontinuation. The VentaProst weaning process should occur in isolation to other treatment changes (no changes in inotropes, pressors, or vasodilators).

Patients will be observed closely before, during and after dosing changes. In the event the patient demonstrates signs of hemodynamic instability (changes in combined hemodynamic parameters) or a decrease in oxygenation indicated by either arterial or central blood oxygenation saturation during downward titration, the VentaProst dose will be returned to its previous level. Once the patient has been stable for 15 minutes, repeat attempts at dose reduction may be undertaken. The process will continue until the patient is fully weaned from VentaProst. The patient will undergo the following study-related procedures and evaluations during VentaProst weaning:

- Stabilize the patient at each dose adjustment for at least 15 minutes
- Measure hemodynamic, oxygenation, and ventilator parameters before and at 15 to 30 minutes after each VentaProst dose adjustment and at 15 to 30 minutes after discontinuation of VentaProst
- Record all concomitant medications
- Record AEs

10.1.5 End of Study (ICU)

Once VentaProst dosing has been discontinued, the patient will undergo the following study-related procedures and evaluations within 24 hours of VentaProst discontinuation:

- Record all concomitant medications
- Record AEs
- Perform comprehensive physical examination
- Obtain vital signs and weight
- Perform 12-lead ECG
- Collect blood for clinical laboratory tests, including serum pregnancy test for women of childbearing potential

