4.3.1 Part I

Individual patient participation is expected to be approximately 5 weeks including:

- Screening: up to 30 days
- Intra-Operative: 3-8 hours
- Aerosolized Veletri Treatment administered in accordance with each site's standard of care guidelines (OR/ICU): 24+ hours (dependent on multiple factors)
- VentaProst Treatment (ICU): 24+ hours (dependent on multiple factors)
- End of Study: 4+ hours (dependent on multiple factors)

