4.6 End of Treatment

In both Part I and Part II, final PD measurements (based on hemodynamic parameters, indices of oxygenation, and ventilator support) will be collected 15 to 30 minutes after discontinuation of VentaProst. End of study physical examination, vital signs/weight, 12-lead ECG, clinical laboratory testing, serum pregnancy testing, hemodynamic parameters, oxygenation measurements, ventilator parameters, adverse events monitoring, and concomitant medications will also be obtained at the end of treatment.

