7.2 Secondary Endpoints

The secondary endpoints that will be assessed include:

- Safety of VentaProst dosing regimen
 - Monitoring of adverse events (AEs), physical examinations, laboratory tests, and electrocardiograms
- Effect of VentaProst dosing regimen on:
 - Cardiovascular Parameters
 - Pulmonary Vascular Resistance (PVR)

- Pulmonary Arterial Pressure (PAP)
- Systemic Arterial Pressure
- Central Venous Pressure (CVP)
- Pulmonary Capillary Wedge Pressure (PCWP)
- Cardiac Output (CO)
- Oxygenation
 - Arterial Oxygen Saturation (SaO_2) or Oxygen Saturation by Pulse Oximetry (SpO_2)
 - Partial Pressure of Oxygen in Arterial Blood (PaO_2)
- Ventilator Support
 - FiO_2
 - Ventilator pressures
 - Ventilator volumes
 - Duration of intubation
- Number and type of cardiovascular medications required through end of study

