8.2 Adverse Events

8.2.1 Definitions

Adverse events are any untoward medical occurrence in a patient administered a pharmaceutical product and which does not necessarily have to have a causal relationship with this treatment. For the purposes of this study, this will include unanticipated medical events in the judgment of the investigator. Expected medical events are untoward clinical occurrences that are perceived by the investigator to occur with reasonable frequency in the day-to-day care of patients who have undergone cardiac surgery with CPB and who are treated in the ICU with mechanical ventilation. Such events will not be considered adverse events unless the investigator considers the event to be associated with study medication, study device, or to be unexpectedly severe or frequent for a patient.

A pre-existing condition or symptom is one that is present at the start of the study and is reported as part of the patient's medical history. A pre-existing condition or symptom should be reported as an AE only if its frequency, intensity or character worsens during study treatment.

All AEs that occur from the time of the first dose of study medication through the End of Study will be recorded and reported as Treatment-Emergent Adverse Events (TEAE). All AEs must be appropriately documented in the patient's medical chart and on the CRFs. When known, investigators should report syndromes rather than list symptoms associated with the syndrome.

All AEs that are ongoing at the conclusion of the study should be followed until: a) resolution/stable sequelae; b) the Investigator determines that it is no longer clinically significant; or, c) the study patient is lost to follow-up. If no follow-up is provided, the Investigator must provide a written justification.

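### End of Study has no fixed time after VentaProst stops, so post-drug capture of new non-serious AEs and cardiovascular medications can differ between patients from under an hour to 24 hours

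*Combined protocol and SAP*

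**What the plan says.** The protocol speaks to the timing of End of Study in three places.

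- Section 4.6 covers both parts. It lists the examination, ECG, laboratory tests and other items, ending with "adverse events monitoring, and concomitant medications will also be obtained at the end of treatment".
- Section 4.3.1 lists, among the phases of participation, "End of Study: 4+ hours (dependent on multiple factors". Section 4.3.2 and the synopsis give the same figure.
- Section 10.1.5 reads: "Once VentaProst dosing has been discontinued, the patient will undergo the following study-related procedures and evaluations within 24 hours of VentaProst discontinuation". Section 10.2.4 uses the same sentence for Part II. Neither gives an earliest time.

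Two collection windows end at that point. Section 8.2.1 sets the first: "All AEs that occur from the time of the first dose of study medication through the End of Study will be recorded". It counts all such events as treatment-emergent. Section 7.2 names the endpoint "Number and type of cardiovascular medications required through end of study".

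Two provisions go further. Section 8.2.1 adds: "All AEs that are ongoing at the conclusion of the study should be followed until". The end points it lists include resolution and stable sequelae. Section 8.2.7 requires SAEs to be reported from the first dose and states no end date.

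**The concern.** When End of Study is completed determines how long a patient is watched for new events after VentaProst stops. A site that completes it soon after the pump stops and a site that completes it a day later both comply with 10.1.5, yet they contribute different observation times to the same table. Sections 12.7 and 12.7.1 summarise AEs as incidence, with no stated allowance for unequal observation. The medication endpoint has the same weakness.

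This matters because the protocol reports no prior clinical trials of VentaProst (2.2.2, 2.2.4) and makes safety and tolerability the first secondary objective (3.2). With about 10 patients per part, one patient whose event falls outside the recorded window moves a reported incidence by 1/10, or 10 percentage points.

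**Working it through.** The protocol gives no figure of its own to reproduce here. The check sets the timing statements side by side and then works out the window lengths they permit.

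**Step 1. Timing statements**

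| Place | Timing of End of Study | Minimum after stop | Maximum after stop |
|---|---|---|---|
| 4.6 | at end of treatment | none stated, effectively 0 h | not stated |
| 4.3.1, 4.3.2, synopsis | phase of 4+ hours | 4 h, if binding | open |
| 10.1.5, 10.2.4 | within 24 hours of discontinuation | none stated | 24 h |

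The 4+ hours entry is a phase length, listed beside the 3 to 8 hours for surgery. It fits a 24-hour limit. It does not fit easily with assessments made at the end of treatment.

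The stated total of about 5 weeks does not settle the matter. For Part I with 8 h of surgery:

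- 4 h End of Study: 30 d + (8 + 24 + 24 + 4) h = 32.5 d, or 4.6 weeks.
- 24 h End of Study: 30 d + (8 + 24 + 24 + 24) h = 33.3 d, or 4.8 weeks.

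Both fit.

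**Step 2. Post-VentaProst tail**

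The last scheduled reading is 15 to 30 minutes after discontinuation (10.1.4.2, 10.2.3.2). I take 0.5 h as a practical early End of Study. This is an assumption, since the protocol does not make that reading a precondition.

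- No binding minimum: 0.5 h to 24 h.
- 4 h binding: 4 h to 24 h, a ratio of 24 / 4 = 6.

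**Step 3. Whole AE window**

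Recording starts at the first dose of study medication, which I read as VentaProst following 6.1. Let T be the time on VentaProst. The protocol lists 24+ hours, so I take T = 24 h and, as assumed alternatives, 12 h and 48 h. The window is T plus the tail.

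| T (assumed) | Tail 0.5 h | Tail 24 h | Ratio |
|---|---|---|---|
| 12 h | 12.5 h | 36 h | 2.9 |
| 24 h | 24.5 h | 48 h | 2.0 |
| 48 h | 48.5 h | 72 h | 1.5 |

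With T = 24 h and a binding 4 h minimum, the window is 28 h to 48 h, a ratio of 1.7.

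**Step 4. Which events are affected**

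SAEs are reportable with no stated end (8.2.7), and AEs already ongoing are followed (8.2.1). What can be lost is a new, non-serious AE, or a new cardiovascular medication, that begins after an early End of Study.

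**Step 5. Classification of events in the tail**

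Section 8.2.1 treats every AE through End of Study as treatment-emergent. Section 12.7.1 defines treatment-emergent as arising, returning or worsening during treatment, and only lists the rest. A new AE six hours after discontinuation is treatment-emergent under the first and arguably not under the second.

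**The case against.** A reader might infer from 24 / 0.5 that safety observation varies 48-fold, or might apply a constant event rate to the tail alone and conclude that incidence could differ many times over. The documents do not support that. The planned incidence counts from first dose, so the spread is that of Step 3, and the protocol gives no event rate.

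A reader might also infer that safety capture stops altogether at End of Study, or that rebound would go unseen. Neither follows. SAE reporting and follow-up of ongoing AEs continue. Weaning is stepwise, with close observation, AE recording and readings at each step and again 15 to 30 minutes after discontinuation (10.1.4.2, 10.2.3.2), and the half-life is given as about three minutes (2.1). Bleeding is described as a theoretical risk in 2.2.5.

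Other objections carry some weight:

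- Section 10 is the detailed schedule and 4.6 a summary, so a site would probably follow the 24-hour rule. That rule still has no minimum.
- No sentence says that completing the examination and blood draw ends AE recording. Equally, none says that recording continues to a fixed time.
- The study is small, open-label and descriptive, with individual listings. This limits the consequence but does not make the windows comparable.
- Time on drug also varies, so fixing the tail does not equalise total observation.

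**Conclusion.** The point stands in a limited form. Section 4.6 conflicts with 10.1.5 and 10.2.4, and no section fixes a cut-off for new AEs or cardiovascular medications. The tail after VentaProst can run from well under an hour, or from 4 hours if 4+ hours is binding, to 24 hours. Over the whole window from first dose the spread is about 2-fold, assuming 24 hours on drug; a longer treatment narrows it and a shorter one widens it.

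The effect falls on secondary safety and medication summaries and leaves the primary endpoint untouched. It is worth correcting because the correction is cheap and the product has no earlier clinical trials.

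The hemodynamic, oxygenation and ventilator readings that 4.6 lists at End of Study, and that Tables 1 and 2 and Sections 10.1.5 and 10.2.4 do not schedule there, are an editorial point. The 15 to 30 minute post-discontinuation readings are already scheduled under the treatment period.

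**What to change.** Separate the collection window from the time of the assessments.

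- In 7.2, 8.2.1, 10.1.5 and 10.2.4, state that new AEs and cardiovascular medications are recorded through a fixed 24 hours after VentaProst discontinuation in every patient, whenever the End of Study examination, ECG and blood draw are done. Twenty-four hours is the protocol's own outer limit.
- Align the synopsis, 4.3 and 4.6 with this.
- Reconcile the treatment-emergent definition in 12.7.1 with 8.2.1, so that events in the 24-hour tail are classified one way.
- Because 5.4.1 moves patients to aerosolized Veletri after extubation, flag in the listings any event that occurs after that crossover.
- Either schedule the extra readings named in 4.6 in the End of Study column or remove them from 4.6.

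The cost is protocol wording and a short chart review at 24 hours, with no added procedure. Some recorded events will occur while the patient is on Veletri, hence the flag. The change standardises the post-drug tail and leaves the variable time on drug as it is.

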10.2 Part II

10.2.1 Screening

Potential study patients will be recruited by the study staff from patients who will undergo cardiac surgery with CPB. Prior to performing any study procedures or assessments, the nature of the study and the potential risks associated with the trial will be explained to the potential study patient and written informed consent obtained. Once informed consent has been obtained, the potential study patient will undergo the following study-related procedures and evaluations:

- Review inclusion and exclusion criteria

- Obtain medical history (including history of any medications within 30 days prior to Screening) and demographics (including date of birth, gender, race, and ethnicity)
- Obtain vital signs, height, and weight
- Perform comprehensive physical examination
- Spirometry – only for those patients with presence or history of significant restrictive or obstructive lung disease
- Perform 12-lead ECG
- Collect blood for clinical laboratory tests, including serum pregnancy test for women of childbearing potential

If the patient meets all the eligibility criteria, the patient may be enrolled into the study. If the patient is not eligible for the study, the patient will be considered a screen failure.

10.2.2 Intra-Operative (OR)

The patient will undergo cardiac surgery with CPB in the OR and the following study-related procedures and evaluations:

- Measure hemodynamic parameters prior to cardiac surgery (after induction) with CPB. These measurements will represent the baseline for hemodynamic parameters
- Record all cardiovascular procedures and concomitant medications
- Investigator assessment of any unanticipated medical events

10.2.3 VentaProst Treatment (OR/ICU)

10.2.3.1 Dosing

The patient will undergo the following study-related procedures and evaluations:

- Patients will receive a starting dose of 3.4 ng/kg/min of VentaProst
- Patients will receive increases in VentaProst dose by 3.4 ng/kg/min (refer to VentaProst Pharmacy Manual)
 - If greater than a 15% improvement in one or more hemodynamic parameters (as defined by the clinical team) is seen with the initial VentaProst dose, but NO additional clinically meaningful change is seen with the first dose escalation, the VentaProst dose will be reduced to the initial dose level
 - If greater than a 15% improvement in one or more hemodynamic parameters (as defined by the clinical team) is seen with the initial VentaProst dose, but AN additional clinically meaningful change is seen with the first dose escalation, continue to dose with VentaProst in increasing steps of 3.4 ng/kg/min every 5 to 15 minutes as clinically indicated until no further improvements in one or more hemodynamic

parameters are achieved or until dose-limiting pharmacological effects are elicited or a tolerance limit to VentaProst is established

- If less than a 15% improvement in one or more hemodynamic parameters (as defined by the clinical team) is seen with first dose increase, continue to dose with VentaProst in increasing steps of 3.4 ng/kg/min every 5 to 15 minutes as clinically indicated until no further improvements in one or more hemodynamic parameters are achieved or until dose-limiting pharmacological effects are elicited or a tolerance limit to VentaProst is established. After the VentaProst has been stabilized, reduce the VentaProst dose to the previous dose level at which a hemodynamic parameter showed maximum improvement. The VentaProst dose level will remain at this setting until clinical conditions determine the need for changing the dose
- Measure hemodynamic, oxygenation, and ventilator parameters at each dose adjustment
- Record all concomitant medications
- Record AEs

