The second part of the study will be conducted in approximately 10 consented cardiothoracic surgical patients requiring CPB with perioperative pulmonary hypertension (pulmonary arterial mean pressure [mPAP] \geq 25 mm Hg). This part of the study is designed to establish a dose response relationship of VentaProst to PD effect by dose escalation in these patients. The goal will be to determine the VentaProst dose necessary to achieve at least a 15% improvement in one or more hemodynamic parameters (as defined by the clinical team).

Hemodynamic measurements will be taken prior to cardiac surgery (after induction) with CPB, prior to dosing with VentaProst, and after each dose titration step.

Qualifying patients will:

- Receive a starting dose of 3.4 ng/kg/min of VentaProst
- Have hemodynamic parameters monitored and recorded
- Receive increase in the VentaProst dose in 3.4 ng/kg/min increments (refer to VentaProst Pharmacy Manual)
 - *IF GREATER THAN A 15% IMPROVEMENT IN ONE OR MORE HEMODYNAMIC PARAMETERS (AS DEFINED BY THE CLINICAL TEAM) IS SEEN WITH THE INITIAL VENTAPROST DOSE, but NO additional clinically meaningful change is seen with this first dose escalation:*
 - Have the VentaProst dose reduced to the initial dose level
 - *IF GREATER THAN A 15% IMPROVEMENT IN ONE OR MORE HEMODYNAMIC PARAMETERS (AS DEFINED BY THE CLINICAL TEAM) IS SEEN WITH THE INITIAL VENTAPROST DOSE, but AN additional clinically meaningful change is seen with the first dose escalation:*
 - Continue to receive VentaProst in increasing steps of 3.4 ng/kg/min every 5 to 15 minutes as clinically indicated until no further improvements in one or more hemodynamic parameters are achieved or until dose-limiting pharmacological effects are elicited or a tolerance limit to VentaProst is established.
 - *IF LESS THAN A 15% IMPROVEMENT IN ONE OR MORE HEMODYNAMIC PARAMETERS (AS DEFINED BY THE CLINICAL TEAM) IS SEEN WITH FIRST DOSE INCREASE:*
 - Continue to receive VentaProst in increasing steps of 3.4 ng/kg/min every 5 to 15 minutes as clinically indicated until no further improvements in one or more hemodynamic parameters are achieved or until dose-limiting pharmacological effects are elicited or a tolerance limit to VentaProst is established.

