¹¹ For those patients with presence or history of significant restrictive or obstructive lung disease

¹² Vital signs and weight only

Table 2 – Schedule of Assessments and Procedures – Part II

Study Procedures	Screening	Intra-Operative	VentaProst Treatment Period (OR/ICU)	End of Study
Written Informed Consent	X			
Demographics	X			
Assign Patient ID	X			
Medical History	X			
Medication History	X			
Physical Examination	X			X
Vital Signs/Weight/Height	X			X ⁹
12-Lead ECG	X			X
Spirometry	X ⁸			
Clinical Laboratory Sampling	X			X
Serum Pregnancy Test	X			X
Inclusion/Exclusion Criteria	X	X		
Cardiac Surgery with CPB		X		
Administer VentaProst			X ⁶	
Hemodynamic Parameters ¹		X ⁵	X ⁷	
Oxygenation Measurements ²			X ⁷	
Ventilator Parameters ³			X ⁷	
AE Monitoring ⁴		X		X
Concomitant Medications	X	X		X

¹ Hemodynamic parameters include, but not limited to, Cardiac Index (CI), Cardiac Output (CO), Central Venous Pressure (CVP), Diastolic Pulmonary Arterial Pressure (dPAP), Diastolic Systemic Arterial Pressure (dSAP), Heart Rate (HR), Mean Pulmonary Arterial Pressure (mPAP), Mean Systemic Arterial Pressure(mSAP), Pulmonary Capillary Wedge Pressure (PCWP), Pulmonary Vascular Resistance (PVR), Rhythm, Systolic Pulmonary Arterial Pressure (sPAP), and Systolic Systemic Arterial Pressure (sSAP)

² Oxygenation measurements include SaO₂ or SpO₂ and PaO₂

³ Ventilator parameters include Ventilator Type, Ventilator Mode, FiO₂, Inspiratory Time, Mean Airway Pressure, Peak Inspiratory Pressure, Positive End Expiratory Pressure, and Respiratory Rate

⁴ To include unanticipated medical events in the judgment of the investigator

⁵ Measure hemodynamic parameters prior cardiac surgery with CPB. Prior to dosing with VentaProst, measure hemodynamic, oxygenation, and ventilator parameters

⁶ Initiate VentaProst at a starting dose of 3.4 ng/kg/min of VentaProst and titrate VentaProst dose up in 3.4 ng/kg/min increments as clinically indicated (refer to VentaProst Pharmacy Manual); stabilize the patient on final dose of VentaProst

⁷ Measure hemodynamic, oxygenation, and ventilator parameters before and after each VentaProst dose change (during dosing, stabilization, and weaning [if still intubated] and at 15 to 30 minutes after discontinuation of VentaProst

⁸ For those patients with presence or history significant restrictive or obstructive lung disease

⁹ Vital signs and weight only

TABLE OF CONTENTS

INVESTIGATOR'S SIGNATURE PAGE	3
1. CLINICAL PROTOCOL SYNOPSIS.....	4

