2.2.2 Clinical Experience

There have been no clinical trials to date with VentaProst.

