6.2.2 Part II

In the OR or the ICU, post-cardiac surgical patients will receive VentaProst at a starting dose of 3.4 ng/kg/min of VentaProst, followed by dose titration up in 3.4 ng/kg/min increments (refer to VentaProst Pharmacy Manual) every 5 to 15 minutes as clinically indicated until clinically meaningful hemodynamic effects are achieved (i.e., at least a 15% improvement in one or more hemodynamic parameters).

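### Part II's dosing tree has no branch for a patient who first reaches 15% at 6.8 ng/kg/min, and the rest of the protocol disagrees on that patient's dose

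*Combined protocol and SAP*

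**What the plan says.** Part II's aim is stated in the synopsis: "The goal will be to determine the VentaProst dose necessary to achieve at least a 15% improvement in one or more hemodynamic parameters". Dosing starts at 3.4 ng/kg/min and rises in steps of 3.4. The branching rule appears in the synopsis, in Section 4.2 and in Section 10.2.3.1.

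- Branch 1 (Section 10.2.3.1) applies when an improvement above 15% "is seen with the initial VentaProst dose, but NO additional clinically meaningful change is seen with the first dose escalation". The dose goes back to the initial level.
- Branch 2 has the same first condition, but the first escalation does add a meaningful change. Escalation continues until improvement stops or tolerance limits it.
- Branch 3 opens "If less than a 15% improvement in one or more hemodynamic parameters (as defined by the clinical team" and goes on: "is seen with first dose increase, continue to dose with VentaProst in increasing steps of 3.4 ng/kg/min". After stabilisation the dose returns to the level of greatest improvement. The synopsis uses the same trigger: "IS SEEN WITH FIRST DOSE INCREASE".

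Two general titration rules appear elsewhere. The Part II treatment entry in the synopsis and Section 4.5 raise the dose until there is no further improvement; the synopsis entry then steps down one level at the plateau. Section 6.2.2 instead titrates "until clinically meaningful hemodynamic effects are achieved (i.e., at least a 15% improvement in one or more hemodynamic parameters". Section 6.3.3.2 has the same target, and Section 6.3.4.2 adds that the dose is then stabilised, with further escalation only for patients who fail to reach it.

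**The concern.** Branches 1 and 2 ask about the response at 3.4 ng/kg/min. Branch 3 asks about the response at the first increase, which is most naturally 6.8. Conditions that test different doses cannot divide patients cleanly. The uncovered patient is an ordinary one: below threshold on the first dose and at or above it on the second. Section 2.1 says Part II is meant to start on the steep part of the dose-response curve, where this pattern would be unsurprising.

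A gap in the tree would matter little if the rest of the protocol gave one clear default, but it gives two. The dose recorded for such a patient can therefore depend on which section the site follows, in the part of the study whose purpose is to find an effective dose. This is also a bedside rule for a new product: Section 2.2.2 says "There have been no clinical trials to date with VentaProst".

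**Working it through.** This is a check of logic; the plan states no figure to reproduce.

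**Inputs (Section 10.2.3.1).** Initial dose 3.4; first increase 3.4 + 3.4 = 6.8; next step 6.8 + 3.4 = 10.2 ng/kg/min. Improvement is taken from baseline, and branch 3 is first read as no parameter having reached 15%.

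**Enumeration.** Three states at the initial dose (below, exactly, above 15%) × two at the first increase (below 15%, at least 15%) × two for an added meaningful change (no, yes) = 12 cells. The last column uses the wording proposed under the fix.

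| Initial dose | First increase | Added change | As written | As proposed |
|---|---|---|---|---|
| <15% | <15% | no / yes | 3 / 3 | 3 / 3 |
| <15% | ≥15% | no / yes | none / none | 3 / 3 |
| =15% | <15% | no / yes | 3 / 3 | 1 / 2 |
| =15% | ≥15% | no / yes | none / none | 1 / 2 |
| >15% | <15% | no / yes | 1 and 3 / 2 and 3 | 1 / 2 |
| >15% | ≥15% | no / yes | 1 / 2 | 1 / 2 |

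As written, 6 cells meet one branch, 4 meet none and 2 meet two (6 + 4 + 2 = 12). As proposed, all 12 meet exactly one (4 in each branch). The cells are not weighted by likelihood.

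**Examples.** 10% then 20% meets no branch. 20% then 12% meets branches 1 and 3.

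**Other readings of branch 3.**

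- *Added gain over the initial dose.* 10% then 20% (gain 10) is now covered. 10% then 26% (gain 16) still meets none, and 20% then 22% (gain 2) meets both 1 and 3 if 2 points is not a meaningful change.
- *Any single parameter below 15%.* The list is long and open (Table 2, footnote 1: "Hemodynamic parameters include, but not limited to, Cardiac Index (CI), Cardiac Output (CO), Central Venous Pressure (CVP" and more). One parameter at 20% then 21% with another at 5% then 5% meets 1 and 3, taking 1 point as not meaningful. Two parameters at 10% then 20% and 8% then 18% meet none.
- *First increase taken to mean the initial dose.* The overlap disappears and 8 cells meet one branch, but the 4 cells at exactly 15% meet none. The tree names the initial dose separately, so this reading is strained.

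**What the other sections tell the 10%-then-20% patient.** Sections 6.2.2, 6.3.3.2 and 6.3.4.2 are satisfied at 6.8. The synopsis treatment entry and Section 4.5 call for 10.2. If 10.2 brings no further improvement, the plateau rule steps back to 6.8 and the two texts agree. If it does, the plateau rule selects at least 10.2 unless tolerance intervenes, which is 10.2 / 6.8 = 1.5 times the dose under the other text.

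**The case against.** The best defence is that escalation is the evident default. The branches sit under a general instruction to raise the dose by 3.4 ng/kg/min, branches 2 and 3 share the same action, and the synopsis and Section 4.5 state the plateau rule outright. A patient who went from 10% to 20% is still improving, so a sensible team would carry on. Much of this stands: continuing is the more natural inference. It does not close the point, because three subsections of Section 6 tell the same team to stop at 15% and nothing says which text governs.

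A reader might also infer from the overlap that the tree gives opposite orders and so sends a falling responder to a different final dose. The documents do not support that. For 20% then 12%, branch 1 reduces and branch 3 escalates, so the next step differs. But branch 3 stops when improvement stops and returns to the dose of greatest improvement, which can be 3.4, the branch 1 dose. On the natural reading the overlap also needs a response that falls as the dose rises, contrary to the premise in Section 2.1.

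The any-single-parameter reading is unlikely in practice, since the clinical team defines which parameters count. Finally, the Appendix 2 schematic is not visible in the copy reviewed and the Pharmacy Manual is not among the documents. Either might clarify the sequence, so the text mismatch is certain but its effect at the bedside is not.

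**Conclusion.** The point holds as a dosing-rule inconsistency that should be corrected. The gap is present under each reading tried; the most charitable one shrinks it to a response of exactly 15%. It matters because the general rules disagree for the uncovered patient, so the selected dose differs between texts whenever improvement continues past 6.8 ng/kg/min. The overlap is secondary and need not change the final dose.

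The reach is limited to the descriptive dose data of about 10 Part II patients. A reader might take the gap to affect a known or large share of them; the documents give no distribution of responses, so no frequency can be stated. Nor is the primary endpoint at risk: it rests on Part I, which has its own titration rule. The conclusion assumes that the first dose increase means 6.8 ng/kg/min and that Appendix 2 and the Pharmacy Manual do not resolve the matter.

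**What to change.** In the synopsis, Section 4.2 and Section 10.2.3.1:

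- Branches 1 and 2: make the first condition *at least 15% in one or more parameters with the initial dose*. This also matches Part II's stated goal, which includes exactly 15%.
- Branch 3: *no hemodynamic parameter has improved by at least 15% with the initial dose*. Moving the test to the initial dose but keeping a shortfall in one or more parameters would not suffice: with 20% in one parameter and 5% in another at 3.4, the branches would still overlap.
- In branches 1 and 2, refer to additional meaningful *improvement* rather than change, so that a falling response belongs to branch 1 only.
- State that the step-back to the dose of greatest improvement applies to every patient who escalates.

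Align Sections 6.2.2, 6.3.3.2 and 6.3.4.2 with the plateau rule, and check that Appendix 2 shows the same sequence. Report for each Part II patient both the first dose reaching at least 15%, which answers the stated goal, and the final selected dose.

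The cost is wording in six places and one summary of two doses per patient. The hemodynamic measurements are already planned at each dose adjustment, so no new measurements or patients are needed. The eCRF is not among the documents, so whether it already captures both doses should be confirmed.
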